### **6.3.2.2 OLE - Early Termination Visit/End of Treatment: Visit**

For subjects who discontinue the OLE Phase of the study for any reason, the assessments detailed in the OLE-ET Visit/EoT Visit should be completed within 2 weeks after the final CC-93538 dose ([Table 6](#)). The OLE-ET Visit will be completed if discontinuation occurs before the Quarterly 4 Visit at the end of OLE Year 2 (OLE Week 104); the OLE-EoT Visit will be completed if discontinuation occurs at or after the Quarterly 4 Visit at the end of OLE Year 2 (OLE Week 104). If the OLE-EoT Visit occurs at the scheduled Quarterly 4 Visit at the end of OLE Year 2 (OLE Week 104), the subject will complete all assessments required for each of the 2 visits collectively

\* Note EGD is required for ET Visits occurring at or before OLE Week 48 but is not required if within 8 weeks since the last EGD. The EGD is not required at ET Visits after Week 48.

(ie, assessments do not need to be repeated). In addition, these subjects should return for the Interim and Final Safety Follow-up Visits ([Section 6.3.1](#)).

The following evaluations will be performed as specified in the [Table 6](#):

- Concomitant therapy
- Assessment of AEs/SAEs
- Hematology, chemistry, and urinalysis
- Urine pregnancy test (only for FCBP)
- Physical examination
- Vital signs
- Serum antibodies to CC-93538
- Serum CC-93538 PK assessment
- Weekly Izumo Scale questionnaire ([Section 6.4.2.1](#)) (only if the visit occurs before or at the OLE Week 48)
- EGID Severity Score (only if the visit occurs before or at the OLE Week 48)
- EGD with tissue biopsies\*

Refer to [Section 6.4](#) for a description of the efficacy assessments conducted throughout the study.

\* Note EGD is required for ET Visits occurring at or before OLE Week 48 but is not required if within 8 weeks since the last EGD. The EGD is not required at ET Visits after Week 48.

## 6.4 Efficacy Assessment

### 6.4.1 Esophagogastroduodenoscopy (EGD)

To ensure quality data and standardization, the same person should perform endoscopic procedures at a study site at each study visit.

The EGD biopsy results for eos count will be read blinded to treatment allocation at a centralized reading facility. Biopsy specimens will be sent to the centralized reading facility, and with the exception of screening, results of the centrally read gastric/duodenal eos count will be blinded to investigative sites during the Induction Phase and the Maintenance Phase. For the OLE Phase, biopsy results on OLE Day 1/Baseline EGD only will be read blinded to treatment allocation and results will also be blinded to investigative sites since this will be same with the EGD conducted either at Week 16 of Induction Phase, during the Maintenance Phase or at Week 48 of Maintenance Phase. A local histologic assessment of EGD biopsy samples should not be performed during the Induction Phase and the Maintenance Phase, unless required for safety reasons (eg, severe EGE flare, AEs, or incidental findings, etc). Any incidental findings of potential clinical relevance that are not directly associated with the objectives of the study should be evaluated and handled by the investigator per the site's standard of care and clinical judgment. More detailed instructions for specimen processing, storage, and shipping will be provided in a separate Study Laboratory Manual.

Endoscopic procedures will be performed as follows:

- EGD will be performed at the time points specified in the Table of Events ([Table 4](#), [Table 5](#) and [Table 6](#)).

Note that [REDACTED] molecular testing through local laboratory assessment may be performed per standard of care and as required per institutional and local guidance prior to the EGD.

- Gastric/duodenal biopsies should be obtained from the following:

#### Stomach

- A set of 4 specimens from separate areas of the gastric antrum (2 to 5 cm proximal to the pylorus)
- A set of 4 specimens from separate areas of the gastric corpus (two from the proximal lesser curvature and two from the greater curvature)
- Up to 1 extra specimen may be collected if there are any additional areas of interest at the judgement of the investigator (if required)
- [REDACTED]

A count of  $\geq 30$  eos/hpf in at least 5 hpfs will be considered diagnostic of EG.

#### Duodenum

- 4 fragments of duodenal mucosa from the second and third part of the duodenum.
- Up to 1 extra specimen may be collected if there are any additional areas of interest at the judgement of the investigator (if required)

– [REDACTED]

A count of  $\geq 30$  eos/hpf in at least 3 hpfs will be considered diagnostic of EGE.

- All subsequent biopsies should be obtained from the same levels as the screening biopsies (ie, stomach and duodenum) maintaining consistency throughout the study.
- Biopsy samples must be obtained ideally from the areas with the most prominent visible abnormalities. For example, if 2-bite biopsies are being obtained, a minimum total of 26 biopsy fragments (from 2 separate 2-bite biopsies) would be obtained from each level.
- The screening EGD must be performed within 8 weeks prior to Day 1. The investigator must document all treatments received at the time of the EGD and biopsy (for any indication) through Day 1, and the subject must not have received any new treatment that might affect EGE since the time of EGD according to protocol requirements (see [Section 8](#)). Subjects should not undergo the screening EGD during the 14-day period just prior to baseline when the final 2 weeks of the screening the Izumo Scale is collected.
- Histologic analysis of the gastric/duodenal biopsy samples for any study-specific assessments will be performed by a central laboratory including enumeration of eos count (peak eos count/hpf) and by analysis of Hematoxylin and eosin (H&E) stained biopsies and gastric biopsies will be graded using the Sydney System on inflammation, metaplasia, atrophy, and reactive gastropathy. The Marsh Scale Classification will be used to grade duodenal samples.
- Histologic analysis includes confirmation of absence of *H. pylori* for gastric biopsies. A highly sensitive monoclonal immunohistochemical stain will be used. If negative, then the subject can participate in the study.

[REDACTED]

[REDACTED]

#### **6.4.2 Clinical Symptoms of EGE**

##### **6.4.2.1 Izumo Scale Questionnaire**

An electronic version of the PRO questionnaire ([APPENDIX B](#)) will be completed weekly by the subject throughout the study. The Izumo Scale questionnaire assesses the comprehensive 5 different GI symptom domains during the past week and consists with 15 weekly questions (3 questions per 1 domain):

- Heartburn Symptoms domain (Questions 1 through 3)
- Gastric Pain Symptoms domain (Questions 4 through 6)
- Stomach Heaviness Symptoms domain (Questions 7 through 9)
- Constipation Symptoms domain (Question 10 through 12)
- Diarrhea Symptoms domain (Questions 13 through 15)

Each question is scored on a scale of “0 = No trouble at all” to “5 = Can't stand it,” and one symptom domain is scored from 0 to 15, with higher values indicating greater symptom severity. Total score is the sum of 5 domains and ranges from 0 to 75.

Three of these 5 domains (Gastric Pain Symptoms domain [Questions 4 through 6], Stomach Heaviness Symptoms domain [Questions 7 through 9] and Diarrhea Symptoms domain [Questions 13 through 15]) are Symptoms of Interest for EGE.

The Izumo Scale Questionnaire was developed in order to evaluate the overall gastrointestinal symptoms and in Japanese as original language ([Furuta, 2009](#)). This is written in easy-to-understand terms in Japanese, and has verified the usefulness by measuring the correlation with Gastrointestinal Symptom Rating Scale ([Svedlund, 1988](#), [Dimenäs, 1995](#)) and the Visual analog scale (VAS) of each symptom in Japanese patients with Functional gastrointestinal disorders (FGIDs) whose symptoms are similar to EGE.

On investigation of 170 Japanese patients with gastrointestinal symptoms, the average scores of Symptoms of Interest (Gastric Pain Symptoms domain, Stomach Heaviness Symptoms domain, and Diarrhea Symptoms domain) on patients with interference with daily activities were 6.17/15, 5.72/15, and 7.36/15, respectively. On the other hand, the average scores of Symptoms of Interest on patients without interference with daily activities were 1.96/15, 2.37/15, and 2.25/15 ([Furuta, 2009](#)). Based on this knowledge, 4/15 for each three domains is set as the threshold for inclusion criteria and clinical responder in this study.

Subjects will complete the Izumo Scale questionnaire weekly during the Screening Period via a handheld device for at least the 2 consecutive weeks before the IP administration on Day 1 (ie, for the final 2 weeks of screening preceding Day 1 that are assessed on Day -7 and Day 1). Every effort should be made to enhance subject adherence to the Izumo Scale Questionnaire completion and limit the amount of missing data, which is critical to ensure interpretability of the Izumo Scale assessment in this study. For example, ePRO instrument's reminder alarms will allow subjects to select the timing for their alarm within a standardized window (at the same time as much as possible) of weekly completion of questionnaire, and ongoing surveillance of weekly completion data will also occur in order to correct any issues as close to real time as possible.

Subjects will not be able to complete a questionnaire more than 3 days before/after it is due and will not be able to go back and make any corrections or changes to the data originally entered. This information will be automatically captured and maintained in the ePRO system of the electronic data capture system (EDC).

The Izumo Scale Questionnaire will be administered at the same time weekly as much as possible via an ePRO instruments from Day 1 through Week 48 (through the duration of the Induction and Maintenance Phases) of the study, through the ET Visit (if applicable), and first year of the OLE Phase and at least for the prior week period (7 days) preceding each of the 2 Safety Follow-up Visits (if applicable) according to the Table of Events ([Table 4](#), [Table 5](#), and [Table 6](#)).

#### **6.4.2.2 EGID Severity Score**

Japanese Society of Pediatric Allergy and Clinical Immunology published guidelines of "Eosinophilic Gastrointestinal Disease Clinical Practice Guidelines for Infants and Adults" in 2020. EGID Severity Score has been proposed as the severity classification to define the criteria for designated intractable diseases in Japan and is included in this guideline ([Eosinophilic Gastrointestinal Disease Study Group, Ministry of Health, Labour and Welfare, 2021](#)).

[figure not shown]
There are 2 forms of EGID Severity Score; for patients  $\geq 20$  years old ([APPENDIX C](#)) and for patients from 2 to 19 years old ([APPENDIX D](#)).

[figure not shown]
The EGID scoring tables used in this study refer to the ones shown in "Eosinophilic Gastro-Intestinal Disorder" disclosed by Japan Intractable Diseases Information Center.

[figure not shown]
The EGID Severity Scores are assessed by the investigator. The EGID Severity Score for patients  $\geq 20$  years old assess the intensity and the frequency of 6 different symptoms (vomiting, dysphagia, anorexia, abdominal pain, diarrhea, bloody stool), 2 clinical laboratory tests (albumin, eos ratio of peripheral blood cells) and 2 medical history items (history of surgery and use of systemic corticosteroid or immunosuppressives). The score ranges from 0 to 82 and the higher the score, the greater the severity. A score of  $\geq 40$  is considered as severe, a score of 15 to 39 as moderate and a score of  $\leq 14$  score as mild.

The EGID Severity Score for patients from 2 to 19 years old also assesses 6 different symptoms (vomiting, dysphagia, anorexia, abdominal pain, diarrhea, bloody stool), 2 clinical laboratory tests (albumin, eos ratio of peripheral blood cells) and general condition, [REDACTED]. The score ranges from 0 to 100 and the higher the score, the greater the severity. A score of  $\geq 40$  is considered as severe, a score of 15 to 39 as moderate and  $\leq 14$  score as mild.

The EGID Severity Score will be assessed according to the time points detailed in the Table of Events ([Table 4](#), [Table 5](#), and [Table 6](#)).

#### **6.4.2.10 *Worsening of EGE Symptoms, EGE Flare, and the EGE Flare Assessment Visit***

Subjects with a worsening of EGE symptoms during the study, either in the Induction Phase, Maintenance Phase, or the OLE Phase will be required to complete the EGE Flare Assessment Visit as shown in the Table of Events ([Table 4](#), [Table 5](#), and [Table 6](#)). Subjects with increased signs and symptoms of EGE are instructed to contact the investigator and/or study staff to determine if an EGE Flare Assessment Visit is warranted.

- Worsening of EGE symptoms is defined as continuous worsening of symptoms for 2 consecutive visits (4 weeks apart) compared to baseline, measured by the weekly Izumo Scale score ( $\geq$  4 weeks of no change from baseline or  $\geq$  4 weeks of worsening from baseline).

An EGE Flare Assessment Visit including safety and efficacy evaluations can occur at any time during the study. An EGD may be required at the EGE Flare Assessment Visit to determine if use of rescue therapy is clinically indicated. Alternatively, if endoscopy is conducted as an intervention during an emergency department visit or hospitalization for a worsening of EGE symptoms or flare, medical record source data including details of the endoscopic procedure should be collected for the EGE Flare Assessment Visit EGD requirement. In addition, all attempts should be made to collect biopsy samples, and these samples should be sent to the central reader for histologic analysis. The results of the centrally read gastric/duodenal eos count will be blinded to investigative sites with the exception of screening during the Induction Phase and the Maintenance Phase. If the results of the gastric/duodenal eos count are required to determine the need for emergent rescue therapy, the results of the gastric/duodenal eos count will be disclosed as long as the investigator requires the result. If the results of the gastric/duodenal eos count will be disclosed in the Induction Phase, the subject is to be discontinued from the study and will not be allowed to enter either the Maintenance Phase or the OLE Phase. (See [Section 3.1.6](#).)

The investigator will confirm if the worsening of EGE symptoms requires rescue therapy and, thus, is deemed a severe EGE flare according to the following protocol definitions.

Any worsening of EGE symptoms during study participation will be documented as an EGE flare.

- A severe EGE flare is defined as any worsening of EGE symptoms including a high intensity episode resulting in an emergency department visit or hospitalization, with need for rescue therapy (eg, including but not limited to concomitant corticosteroid therapy over the baseline dose), or a worsening of EGE symptoms for 2 consecutive visits (4 weeks apart) resulting in the need for rescue therapy.
- A mild to moderate EGE flare is defined as any worsening of EGE symptoms without the need for rescue therapy. Concomitant use of systemic corticosteroid therapy with or under the baseline dose of concomitant corticosteroid treatment is not considered as rescue therapy.

During the OLE Phase, subjects who demonstrate a persistent lack of improvement or worsening of EGE symptoms should be evaluated to determine if continuing the study treatment is appropriate. While subjects will have the opportunity to continue participation in the OLE with use of rescue therapy as needed, based on clinical judgment, the investigator should discontinue any subject in which study participation no longer is in the best interest of the subject.

The ET visit or the OLE-ET/EoT procedures performed at the EGE Flare Assessment Visit do not need to be repeated for subjects who discontinue the study prematurely due to an EGE flare.

Subjects who are discontinued from the Induction Phase, the Maintenance Phase or the OLE Phase will be asked to complete an ET visit or an OLE-ET/EoT Visit ([Section 6.2.2](#) and [Section 6.3.2.2](#)) and the 2 Safety Follow-up Visits ([Section 6.3.1](#)).

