**Table 2: Study Endpoints: Induction and Maintenance Phase Endpoints Through Week 48**

Endpoint	Name	Description	Timeframe
Secondary (continued)	Clinical responder definition	Proportion of subjects who achieve < 4/15 in each of three Symptoms of Interest scores using the Izumo Scale from baseline  Gastric Pain Symptoms domain, Stomach Heaviness Symptoms domain, and Diarrhea Symptoms domain are Symptoms of Interest of EGE	Weeks 16 and 48
	Clinical response: Eosinophilic gastrointestinal disorder (EGID) Severity Score	Changes in total score of EGID Severity Score consisting of 8 symptom/laboratory scores and 2 medical history related questions using EGID Severity Score ( APPENDIX C for subjects ≥ 20 years at the time of signing the informed consent form [ICF]) or consisting of 8 symptom/laboratory scores and 3 general condition related questions ( APPENDIX D for subjects from 12 to 19 years at the time of signing the ICF/assent) from baseline	Weeks 16 and 48
	Time to event	The time to event of EGE flare	Through Week 48
	Time to event	The time to event of use of rescue therapy	Through Week 48
	Time to event (subjects who use concomitant treatment only)	The time until concomitant corticosteroid use to zero (and continued by Week 48)	From Week 16 through Week 48
	Proportion of subjects with event (subjects who use concomitant treatment only)	The proportion of subjects for whom the dose of concomitant steroids is reduced to zero	Weeks 24, 32, 40, and 48
	Pharmacokinetics (PK)	Trough concentrations of CC-93538 through Week 48	Through Week 48

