### OLE Phase

During the OLE Phase, subjects who demonstrate a persistent lack of improvement, worsening of EGE symptoms or severe EGE flare should be evaluated if continuation of study treatment is appropriate. While subjects will have the opportunity to continue participation in the OLE Phase with use of rescue therapy as needed, based on clinical judgment, the investigator should discontinue any subject if study participation no longer is in the best interest of the subject. Subjects who are discontinued from the OLE Phase will be asked to complete an OLE-ET/EoT Visit ([Section 6.2.2](#)) and the two Safety Follow-up Visits ([Section 6.3.1](#)).

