## **9 STATISTICAL CONSIDERATIONS**

### **9.1 Overview**

This is a Phase 3, multicenter, randomized, double-blind, placebo-controlled induction and maintenance study to assess the efficacy and safety of CC-93538 in adult and adolescent subjects with EGE. The study will incorporate a 16-week Induction Phase followed by a 32-week Maintenance Phase and an OLE Phase. Subjects will be randomized according to the following stratification factor: concomitant steroid use (yes or no). An independent DMC will be used to review the safety data regularly during the course of the study.

A primary database lock will be performed when all randomized subjects in this study have completed Week 48 of the Maintenance Phase or discontinued the study, including all Safety Follow-up Period data available to date. Analyses in the primary clinical study report (CSR) will be based on this database.

Analysis details not explained in the statistical section of the protocol will be provided in the Statistical Analysis Plan (SAP).

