##### Dichotomous variables:

- The proportion of responders defined as subjects who achieve both clinical and histologic response (Weeks 16 and 48):
  - Clinical response is defined as the proportion of subjects achieve  $< 4/15$  in all Symptoms of Interest (Gastric Pain Symptoms domain, Stomach Heaviness Symptoms domain, and Diarrhea Symptoms domain) of the Izumo Scale
  - Histologic response is defined as a  $> 75\%$  reduction of peak gastric and/or duodenal eos count from baseline

- The proportion of subjects achieving eosinophilic histologic response defined as a > 75% reduction of peak gastric and/or duodenal eos count from baseline (Weeks 16 and 48)
- The proportion of subjects who achieve < 4/15 in all Symptoms of Interest (Gastric Pain Symptoms domain, Stomach Heaviness Symptoms domain, and Diarrhea Symptoms domain) of the Izumo Scale (Weeks 14 to 16, 30 to 32, and 46 to 48)
- The proportion of subjects for whom the dose of concomitant steroids is reduced to zero (Weeks 24, 32, 40, and 48)

The analysis of the response endpoint will be conducted on the ITT population using the Cochran-Mantel-Haenszel (CMH) test stratified by concomitant corticosteroid treatment at baseline (yes or no). In case the Mantel-Fleiss criterion is not met, the Fisher's exact test will be performed instead of the CMH test. For treatment comparison between a CC-93538 dose and placebo, the 2-sided 95% stratified Newcombe CI ([Yan, 2010](#)) for the difference in proportions using the CMH weights will be provided. Missing data and any observed data after rescue therapy/prohibited medication which may impact the efficacy assessment will be set as non-responders.

Time to event data:

- The time to event of EGE flare (Through Week 48)
- The time to event of use of rescue therapy (Through Week 48)
- The time until concomitant corticosteroid use to zero (From Week 16 through Week 48)

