For the time-to-event endpoints, the numbers of subjects who have an event will be summarized. The Kaplan-Meier (KM) estimates of the 25th, median, and 75th percentile of the time to the first event and the 2-sided 95% CIs will be provided. The cumulative number of events, the number of subjects at risk, and the KM estimate of the event rate (i.e., failure probability instead of survival probability) and SE will be provided by time point. The KM plot of failure curves (instead of survival curves) with the number of subjects at risk at each time point will be presented. To test the KM curve in the treatment group is different from that in the placebo group in at least one stratum, a stratified log-rank test will be conducted.

Multiplicity Adjustment

Only one formal statistical test will be performed for the primary endpoint. For any other comparisons, nominal p-value (without adjustment for multiplicity) will be provided as a measure of the strength of association between the endpoint and the treatment effect rather than a formal statistical test. Therefore, the multiplicity adjustment is not applicable in this study.

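### Section 6.4.2.10 contradicts itself on worsening, so time to first EGE flare can, as written, count subjects who only fail to improve

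*Combined protocol and SAP*

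**What the plan says.** Section 6.4.2.10 opens its definition with "Worsening of EGE symptoms is defined as continuous worsening of symptoms for 2 consecutive visits (4 weeks apart) compared to baseline". It says this is measured on the weekly Izumo score and then gives two alternatives in parentheses: at least "4 weeks of no change from baseline or" at least 4 weeks of worsening.

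The same section, and Section 3.1.6, then state: "Any worsening of EGE symptoms during study participation will be documented as an EGE flare". Worsening that needs no rescue is classed as a mild to moderate flare, so the absence of treatment does not stop an episode from being a flare.

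Table 2 lists "The time to event of EGE flare" as a secondary endpoint through Week 48. Section 9.6.3.1 analyses it by Kaplan-Meier with a stratified log-rank test and reports "The Kaplan-Meier (KM) estimates of the 25th, median, and 75th percentile of the time to the first event". Neither place restates or narrows the event. Section 9.1 leaves unexplained analysis detail to a separate SAP, whose text is not available here.

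**The concern.** A flare endpoint is normally read as time to deterioration. Inclusion criterion 4 requires a score of at least 4/15 in a Symptom of Interest domain, so subjects start symptomatic, and one who stays at that level has not improved but has not deteriorated either. If that counts as a flare, three things follow:

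- The curve mixes non-response with deterioration.
- Because only the first event is analysed, an early no-change event keeps a later true deterioration out of the analysis.
- If the drug improves symptoms, no-change events would fall more often on placebo. The log-rank comparison would then partly repeat the symptom response that the Izumo endpoints already measure, under the name of flare.

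Flare frequency, named in the same secondary objective in Table 1, would inherit the problem.

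**Working it through.** The plan states no event count, rate or power for time to flare, so there is no figure to reproduce on this point. The only sizing figure, 39 evaluable and 45 enrolled (Section 9.3), belongs to the primary endpoint. It reproduces with an exact two-sample t-test: difference/SD = 70/70 = 1, 2:1 allocation, two-sided 0.05. Power is 78.5% at 24 + 12 = 36 and 81.8% at 26 + 13 = 39. Allowing for 10% dropout, 39/0.9 = 43.3, so 44, or 45 as a multiple of 3. Nothing in it depends on the flare definition.

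The rest is a reading of the definition chain.

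1. **Worsening.** The lead clause of Section 6.4.2.10 needs worsening at two visits. The measurement rule joins no change and worsening with *or*, so no change alone satisfies it. The two halves cannot both be the rule, and the section does not say which governs.
2. **Flare.** Any worsening becomes a flare (Sections 3.1.6 and 6.4.2.10). If the measurement rule governs, no change becomes a flare.
3. **Endpoint.** Table 2 and Section 9.6.3.1 take the flare as it stands and use the first one.
4. **Timing for one subject.** Table 4 puts visits on Day 1, Day 29 (Week 4) and Day 57 (Week 8). Take a subject with an identical Izumo score throughout:
   - four-week reading: event at Week 4, and 4/48 = 8.3% of the window;
   - two-visit reading: event at Week 8, and 8/48 = 16.7% of the window;
   - score increase in both cases: 0.
5. **Number of such subjects.** Not computable. The documents give no rate of no change or of worsening. They also do not say whether the score is a domain or the total, or how close to baseline counts as no change.
6. **Conduct.** Two-visit worsening bars entry to Maintenance (Section 6.4.2.11) or ends participation in it, with possible entry to the OLE (Section 3.1.6). Both refer back to Section 6.4.2.10, so on the same reading a no-change subject may leave the blinded phase. If no change is removed from the event and nothing else is done, that subject is censored at exit for a reason tied to outcome.

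**The case against.** The strongest reply is that the lead clause controls. Section 6.4.2.11, applying the same definition, repeats only the continuous-worsening wording, and Sections 3.1.4 and 3.1.6 say only worsening. The severe-flare definition also names any worsening and two-visit worsening as separate limbs, so the sentence that turns any worsening into a flare may use the word in its ordinary sense, which excludes no change. This stands as a possible reading. It does not remove the problem, because the text does not choose and two sites could record the same subject differently.

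Second, event derivation belongs in a SAP, and the amendment history shows that one exists. That also stands: a narrower definition there would settle the analysis, but it cannot be confirmed here.

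Third, subjects are told to contact the site when symptoms increase, so stable subjects may seldom be recorded as flares. That is plausible, but it makes the event depend on site practice.

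Fourth, the stakes are limited. This is a secondary endpoint outside the key set, with nominal p-values. Time to rescue therapy is a separate endpoint, so deterioration that needs treatment is captured independently. This is correct and limits the weight of the point.

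A reader might also cite the OLE text in Section 3.1.6, which lists "subjects who demonstrate a persistent lack of improvement, worsening of EGE symptoms or severe EGE flare", as proof that non-improvement and worsening are separate states. It is only weak support: severe flare is itself a form of worsening and is listed separately too, and the text governs continuation of OLE treatment, not the Week 48 endpoint.

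**Conclusion.** The definition is internally inconsistent. Followed as written, its measurement rule lets time to first flare count subjects with no deterioration. That rests on the measurement rule governing and on the SAP not narrowing the event. The size is unknown; the only figures the text supports are the Week 4 or Week 8 event times for a subject with an unchanged score. The primary endpoint and the sample size are unaffected.

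Two stronger readings are tempting and unsupported. One is that every non-improver will be a flare and the endpoint cannot be read as deterioration at all. The lead clause, the unseen SAP and the unknown recording practice do not allow that. The other is that Section 3.1.6 should confine mild to moderate flares to worsening short of the two-visit rule. Because the current definition of worsening is itself the two-visit rule, that sentence would empty the category.

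**What to change.** For the time-to-flare analysis, define the event as either:

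- an increase from baseline in the weekly Izumo score in at least one Symptom of Interest domain (gastric pain, stomach heaviness, diarrhea), sustained over the two-visit, 4-week rule; or
- a high-intensity episode leading to an emergency visit or hospitalization and needing rescue therapy.

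Do not count no change as an event. State the smallest increase that counts; the documents give no minimal important change, so the sponsor must set it. Report 4 or more weeks of no change separately as lack of improvement, and keep it as a trigger for clinical evaluation. If the SAP already has such a definition, a cross-reference from Section 9.6.3.1 is enough for the event itself.

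Because no-change subjects may still be barred from Maintenance or leave it for the OLE, do not handle that exit only as non-informative censoring. Add a sensitivity analysis that counts it as a competing or composite event.

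The weekly Izumo data are already collected. The cost is fewer flare events, hence less information on this endpoint, and one additional sensitivity analysis.
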